1 PROTOCOL SUMMARY

1.1 SYNOPSIS

Title:	Initial Testing of Whole Health STEPS (Structured Tiered Engagement with Peer Support)
Grant Number:	1 IK2 RX003390-01A1
Study Description:	This two-phase pilot trial (open trial followed by pilot RCT) is designed to evaluate the feasibility and acceptability of Whole Health STEPS.
Study Population:	The target population is primary care Veterans with mental health symptoms who are not engaged in mental health care.
Description of Intervention:	Whole Health STEPS (Structured Tiered Engagement with Peer Support) is a peer-delivered wellness service designed for delivery in VA primary care settings.

1.2 SCHEMA

2 INTRODUCTION

2.1 STUDY RATIONALE

Functional impairment, limitation in social and occupational roles (Üstün & Kennedy, 2009), is a significant problem for Veterans. Across diagnostic categories, mental health symptoms are associated with functional impairment and difficulty with role-related task (Kazis et al., 1998; Löwe et al., 2008; Spitzer et al., 2006). Despite the availability of services, many Veterans with mental health symptoms do not engage in mental health treatment (Elbogen et al., 2013; Seal et al., 2010). ***Whole Health STEPS (Structured Tiered Engagement with Peer Support) is an innovative approach to engaging this population through combining two novel modalities to engage with Veterans, peer support and Whole Health, tailored for delivery in Primary Care Mental Health Integration (PCMHI) a platform designed to increase access to mental healthcare.***

This two phase pilot trial is designed to address two key objectives (1) evaluate the feasibility and acceptability of Whole Health STEPS and (2) evaluate the preliminary impact of Whole Health STEPS on patient outcomes.

- Phase 1 addresses objective 1 and will be an open trial (Eligible n=10) to test the feasibility of peer delivery in primary care and acceptability to Veterans to inform further manual adjustments. Feasibility of research procedures will also be evaluated to inform adjustments to the research protocol.
- Phase 2 addresses objective 2 and will be a pilot RCT with a waitlist control (Eligible n=44) to evaluate impact on functional impairment and feasibility for subsequent grant applications.

2.2 BACKGROUND

Peers within VA are Veterans in recovery from mental illness with specialized training to support other Veterans with mental health concerns (Chinman et al., 2013). Within the context of their job duties, peers perform a number of functions including sharing their mental health recovery story, advocating for Veterans, acting as role models, providing crisis support, acting as liaisons with staff, providing outreach, supporting treatment, teaching coping skills, supporting patient engagement for patients with mental health concerns, and wellness coaching (Chinman et al., 2013; Swarbrick et al., 2016). Benefits from peer services include functional outcomes such as quality of life, socialization, recovery/hope, fatigue/sleep, daily functioning, and healthcare engagement (Chinman et al., 2014; Davidson et al., 2006; Druss et al., 2010; Lorig et al., 2014).

Whole Health is a patient-centered model of care within VA (Krejci et al., 2014) which incorporates a range of services with a range of intensities appropriate for peer-delivery. Early research within the VA on Whole health interventions suggests high acceptability and Veteran improvements on a broad range of outcomes including psychological well-being, mental health symptoms, physical health, ability to engage in valued activities, and wellness domains (Denneson et al., 2019; Hull et al., 2019; Mori et al., 2019).

PCMHI is a platform of care which significantly increases access and utilization of mental health services for primary care Veterans, but some Veterans still do not engage in care due to low mental health problem recognition and negative beliefs about psychotherapy (Johnson & Possemato, 2021; Kehle et al., 2011; Possemato et al., 2018; Wray et al., 2012). Peer support and Whole Health are well positioned

to address those barriers and be adapted for delivery in PCMHI using a stepped care model. Stepped care interventions are designed to offer the least intensive intervention that is likely to provide benefit and involve systematic monitoring of progress to increase the level of care as needed to “self-correct” (*Bower & Gilbody, 2005*). Preliminary evidence from a prior trial of Peer-Delivered Whole Health Coaching (*Johnson et al., 2021*) suggested positive results from a peer-delivered Whole Health approach and informed the stepped care design including the addition of lower intensity interventions as early steps and the frequency and duration of the intervention.

3 STUDY DESIGN

3.1 OVERALL DESIGN

This study consists of a two phased clinical trial.

Phase 1 is an open trial establishing preliminary feasibility and acceptability of Whole Health STEPS and informing adjustments to the clinical manual. Participants will be followed for the duration of their participation in Whole Health STEPS, a period of approximately 2-3 months. Following phase 1 enrollment, the investigators will review the data, make adjustments to the Whole Health STEPS manual and research protocol as necessary, and proceed with enrollment in Phase 2.

Phase 2 is a 2-arm single-site pilot randomized clinical trial with a waitlist control evaluating Whole Health STEPS impact on patient outcomes and feasibility. Random assignment will be made by research staff following eligibility determination using a stratified permuted block design based on baseline functional impairment (mild-moderate functional impairment $IPF \leq 50$ vs. severe-extreme functional impairment $IPF \geq 51$). Participants will be followed for a period of approximately 4-5 months, 2-3 months will be participation in Whole Health STEPS and 2 months will be either be waitlist or follow-up depending on randomization outcome.

- Hypothesis 2a. Whole Health STEPS will demonstrate an effect size (d) > 0.3 on psychosocial functioning.
- Hypothesis 2b. Whole Health STEPS will demonstrate clinical feasibility including positive results on process outcomes, retention, fidelity, and appropriateness on stepped-care decision points.

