4.2 EXCLUSION CRITERIA

An individual who meets any of the following criteria will be excluded from participation in this study:

Exclusion Criteria	Operational Definition
1. Actively engaged with an equivalent or higher level of care with the exception of medication management for mental health concerns	Pending or planned future appointments in: 
 Whole Health Coaching/Peer Support or other individual coaching/support for health, wellness, or lifestyle changes PCMH Outpatient psychotherapy Peer support
2. Preference for direct referral to mental healthcare	Veteran answers affirmatively to the question "Would you prefer a referral for mental health services rather than participate in this trial?"
3. Recent changes to psychotropic medications	Change in medication type or dose within the last 2 months to a psychotropic medication or a medication prescribed for mental/behavioral health concerns
4. Severe impairment preventing engagement with a peer, warranting direct referral to a licensed independent provider for monitoring	
 High risk based on the P4 screener, and/or Significant cognitive impairment (BOMC $>$ 10), and/or

and follow-up, and/or affecting ability to complete research tasks.	
 • Need for accommodations that would invalidate research measures, and/or • Inability to sustain attention/concentration to complete questionnaires, interviews, and/or peer sessions, and/or • Other significant concerns about impairment.
5. Inability to independently communicate in verbal and written English	Demonstrates inability to understand and respond to research interviews and self-report assessments during the baseline in English, without assistance from a translator or interpreter.

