6 ASSESSMENT PLAN

Assessments will be conducted with Veterans in person, over the phone, or electronically using Qualtrics or REDCap (Research Electronic Data Capture) depending on format of the assessment, safety guidelines for in person meetings, and Veteran preference. Electronic data collection will be the primary data collection strategy but as a contingency plan if electronic administration is not feasible, staff will make every effort to collect the data in an alternate format (paper or oral format) to reduce data loss. If paper format is used, it will be returned in person or via pre-paid envelope. Research staff will call, text using a VA iPhone and/or send an SMS text via Qualtrics or REDCap, and/or send e-mails via a no-reply, Qualtrics or REDCap generated email address to remind participants to complete assessments as needed. See [Data Security Plan](#) for Qualtrics and REDCap security information. Email and text reminders will follow current VA guidance on information security procedures for these communication methods. If oral format is used, it will be through phone, VA approved video-conferencing format, or in person. As a safety precaution, when conducting assessments virtually, research staff will also confirm a phone number for call back, a physical address for where the Veteran is at that moment, an emergency contact person/phone number in case the Veteran has a medical or mental health emergency while on the phone, and two identifiers to confirm the Veteran's identity.

Electronic medical records data collection will be facilitated by research staff with recruitment activities occurring monthly and outcome data collection occurring at the end of the trial. Upon initial recruitment screening, baseline interviews will be scheduled to review consent and HIPAA information and to determine eligibility. If the Veteran chooses to participate in the study and appropriately answers comprehension questions, research staff will document verbal consent on the approved verbal informed consent script. This modification will reduce burden on participants by eliminating the requirement to travel for a baseline assessment to administer written consent and increase the feasibility of the research trial by broadening the population who will be able to participate.

After obtaining verbal consent, research staff will administer the following assessments at the specified timepoints:

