Construct/ Function	Assessment	Recruitment Admin Data	Baseline Part 1	Baseline Part 2	Each Session or Post-Session	Mid Assessment	Final Assessment	Post-Treatment*	Post-Study Admin Data
Sample Description, Recruitment, & Screening	EMR Patient Identifiers and Contact Information	X							
	Self-Report Contact Information		X						
	EMR Demographics	X							
	EMR Mental Health Screeners & Relevant Diagnoses	X							
	EMR Veteran Status	X							
	EMR Primary Care Team Information								
	EMR Medications	X							
	EMR Problem List	X							
	BOMC (for cognition/ orientation)		X						
	P4 Screener (for suicidality)		X						
	Preference for direct referral to behavioral health		X						
	Demographics Questionnaire			X					
Psychosocial Functioning (Primary Patient Outcome)	IPF (psychosocial functioning)		X			X	X		
Behavioral Health Symptoms	PHQ-9 (depression)		X			X	X		
	GAD-7 (anxiety)		X			X	X		
	LEC (PTSD)		X						
	Criterion A Assessment (PTSD)		X						
	PCL-5 (PTSD)		X			X	X		
	AUDIT (alcohol use)		X			X	X		
Other Peer Services Outcomes	EMR VA Healthcare and Social Services Appointments	X							X
	Self-Report non-VA Healthcare and Social Services Utilization		X			X	X		
	RAS-SF (recovery)			X		X	X		

	WAI (therapeutic relationship)							X	
Other Whole Health Outcomes	MILM (meaning in life)			X		X	X		
	QOLI (quality of life)			X		X	X		
	ACORN (resources)			X		X	X		
	WHGAT (Whole Health Goal Attainment)				X				
Whole Health STEPS Feasibility	Intervention retention								X
	Fidelity Checklist				X				X
	Peer Post-session feedback forms (also falls under acceptability)				X				
	Supervisor Post-session feedback forms (design/manual usability)				X				
	UE-ATR (safety)								
Whole Health STEPS Acceptability	Veteran post-session feedback forms				X				
	Veteran post-treatment feedback interview							X	
	CSQ (satisfaction)							X	
Research Feasibility	Recruitment and eligibility rates								
	Data Collection & Procedural Problems								
	Research retention								X

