6.2 PARTICIPANT PAYMENT

Participants will be compensated at a rate of approximately \$20 per hour for research activities (i.e., interviews and self-report assessments). This compensation rate is the rate used for similar behavioral health clinical trials at the Syracuse VA and does not appear to lead to undue influence or coercion.

Compensation will occur through established VA payment procedures approved for research activities (e.g., direct deposit or via a VA debit card). Research staff will collect the minimum required identifiable information to properly process their payments (e.g., if research staff need bank account information to complete a direct deposit form, they will collect the necessary information for the form). Veterans will not be compensated for intervention appointments (i.e., Whole Health STEPS appointments with peers). The compensation for each of the study activities is detailed below.

Open Trial Study Activity	Estimated Burden	Compensation
Baseline Part 1 Consent & Eligibility Determination	~ 1 hour	\$20
Baseline Part 2 Remaining Assessments	~ 1 hour	\$20
Post Session Rating Forms (approximately 6 over the study)*	~ ¼ hour each *6 total = ~1.5 hours	\$5 each *6 total = \$30
Mid and Post Treatment Assessment	~1½ hour	\$30
Post Treatment Interview	~ ½ hour	\$10

* To reduce administrative burden with processing multiple payment vouchers for small amounts, the post-session rating forms will be paid in a lump sum at the end of the study along with the post-treatment interview payment unless participants request a different payment schedule.

RCT Study Activity	Estimated Burden	Compensation
Baseline Part 1 Consent & Eligibility Determination	~ 1 hour	\$20
Baseline Part 2 Remaining Assessments	~ 1 hour	\$20
Mid Assessment	~ 1 hour	\$20
Final Assessment	~ 1 hour	\$20
Post Treatment Assessment (added to either Mid or Final Assessment depending on randomization, or administered ASAP after a participant ends peer support services)	~ ½ hour	\$10
Post Treatment Interview	~ ½ hour	\$10

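### The randomisation trigger in 3.1 does not require Baseline Part 2 to be finished, so the baselines for RAS-SF, MILM, QOLI and ACORN may be collected after the participant knows the arm

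*Combined protocol and SAP*

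**What the plan says.** Section 3.1 states the timing of allocation in the RCT phase: "Random assignment will be made by research staff following eligibility determination using a stratified permuted block design based on baseline functional impairment". It names no other precondition.

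The RCT table in 6.2 divides the baseline into two separately paid blocks of about one hour each: "Baseline Part 1 Consent & Eligibility Determination" and "Baseline Part 2 Remaining Assessments". Section 6 agrees on the purpose of the first contact: "baseline interviews will be scheduled to review consent and HIPAA information and to determine eligibility".

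In the section 6 assessment schedule, "RAS-SF (recovery)", "MILM (meaning in life)", "QOLI (quality of life)" and ACORN (resources) are marked at Baseline Part 2, Mid and Final, with no mark at Part 1. The IPF, labelled there as the primary patient outcome, is marked at Part 1, Mid and Final. So are PHQ-9, GAD-7, PCL-5 and AUDIT.

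Section 3.3 describes the control as a 2-month wait before the same service. Section 11 says patient outcomes will be modelled to give an effect size for comparison with d = 0.3, but specifies no model and no use of baseline values.

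**The concern.** A baseline serves as a baseline only if allocation cannot have influenced it. In a waitlist design the participant cannot be masked once told the arm. Someone who has just heard that the service starts now, or only in two months, may rate recovery, meaning, quality of life or resources differently because of that news. Randomisation does not balance this away, because the disturbance arises after allocation and can differ by arm.

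A second consequence is missing data. A Veteran who is allocated and then leaves before Part 2 is a randomised participant with no baseline on any of the four scales. With 44 eligible Veterans planned for the RCT (section 2.1), each such loss is 1/44 = 2.3% of the sample.

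**Working it through.** The plan states no figure that can be reproduced here. The check is mainly one of order, followed by a conditional calculation of size.

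**Order of procedures**

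1. Allocation follows eligibility determination (3.1).
2. Eligibility determination belongs to Part 1 (6.2, RCT table). As a cross-check, the instruments named in 4.1 and 4.2 are IPF, PHQ-9, PCL-5 with LEC, GAD-7, AUDIT, P4, BOMC and the referral-preference question. All are marked in the Part 1 column of the schedule.
3. Nine self-report outcome scales are repeated at Mid and Final. Five have their baseline in Part 1 (IPF, PHQ-9, GAD-7, PCL-5, AUDIT). Four have it in Part 2 only (RAS-SF, MILM, QOLI, ACORN).
4. No readable section requires Part 2 to be complete before allocation, or the arm to be withheld until then.

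The sequence Part 1, allocate, disclose, Part 2 would therefore comply with the protocol. So would Part 1, Part 2, allocate, disclose. The order is left open for four scales and does not arise for the other five.

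**Size, under assumptions**

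Let δ be the difference between arms in the Part 2 baseline caused only by knowledge of the arm, in SD units. Suppose it does not carry over to the Mid score. Let r be the baseline-to-Mid correlation, with equal SDs at the two times, so that the ANCOVA slope is about r. Neither δ nor r is in the documents; the ranges δ = 0.1 to 0.2 and r = 0.5 to 0.7 are assumptions.

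| Analysis of the four scales | Absolute bias | Range (SD) | Share of 0.3 |
|---|---|---|---|
| Mid score, no baseline used | 0 | 0 | 0% |
| Change from baseline | δ | 0.1 to 0.2 | 0.1/0.3 = 33% to 0.2/0.3 = 67% |
| ANCOVA on baseline | r × δ | 0.5 × 0.1 = 0.05 to 0.7 × 0.2 = 0.14 | 0.05/0.3 = 17% to 0.14/0.3 = 47% |

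The sign depends on which arm's ratings move and in which direction, and the documents give no basis for predicting that.

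**The case against.** The strongest reply is that this is silence, not error. The word used in 3.1 sets an earliest point for allocation; it does not mean immediately afterwards. Both parts are called baseline, and the same two-part split appears in the open trial, where nobody is randomised, so the split was not drawn as a randomisation boundary. It may simply spare ineligible Veterans the second hour. The schema in 1.2 may show the order, and the documents do not say when participants learn their arm. Some exclusion judgements in 4.2, such as sustaining attention through questionnaires, could run into Part 2. All of this stands, except that 6.2 explicitly labels Part 1 as the eligibility step. It limits the point to an order that is not secured.

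A reader might infer three stronger things that the documents do not support:

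- **That the primary result is compromised.** The IPF is both stratifier and primary patient outcome and is taken in Part 1. Hypothesis 2a, with d > 0.3, concerns psychosocial functioning only. Section 11 applies d = 0.3 to patient outcomes generally, which is the only link between that benchmark and the four scales.
- **That the bias reaches two thirds of the benchmark whatever the analysis.** That is the change-score maximum under an assumed shift. The ANCOVA maximum is 47%, and an analysis that ignores baseline is unaffected.
- **That upcoming assignments can be guessed and eligibility steered through the open-ended exclusion "Other significant concerns about impairment".** The documents give no block size, do not say that it is fixed or known to staff, and do not say who can see the list. They also do not say that one person both judges eligibility and assigns; research staff is a job category. This is missing detail, not a demonstrated route to selection bias.

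**Conclusion.** The concern holds in a limited form. The readable protocol permits the baselines of four secondary self-report scales to be collected after an arm that cannot be masked has been disclosed, or to be lost between allocation and Part 2. It does not establish that this is the intended practice. The consequence is confined to change or baseline-adjusted analyses of RAS-SF, MILM, QOLI and ACORN. Its true size and direction are unknown; the 0.05 to 0.2 SD range above rests wholly on the assumed shift and correlation.

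For a single-site pilot with a feasibility focus this is a modest point. It is still worth acting on, because the remedy is nearly free and the problem cannot be repaired in analysis once the data are collected.

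**What to change.** Amend 3.1 to read: *Random assignment will be made after eligibility is recorded and Baseline Part 2 is complete, and the participant is told the arm only then.* Check that the schema in 1.2 shows the same order.

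The cost is one sentence, a short delay to allocation, and a few eligible Veterans lost before rather than after randomisation. If this is already the practice, the change only records it.

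As a separate request for clarification, the sponsor could state how the allocation list is concealed, who has access to it and how block sizes are chosen.

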3.2 STUDY INTERVENTION DESCRIPTION: WHOLE HEALTH STEPS

Whole Health STEPS is a stepped care package incorporating a range of Whole Health peer services into one structured protocol designed to be delivered by a peer in primary care. The whole package is designed to take place over approximately 2-3 months with regular contact with the peer to evaluate the need to increase/decrease the intensity of peer support. Levels of support include supported self-management in which the Veteran completes a self-directed Whole Health tool (i.e., the Personal Health Inventory) and gets regular calls from a peer to check-in about progress, brief telephone support in which the peer asks additional questions to support Veterans’ progress (e.g., inquiry about personal meaning, focus, goals), and full length peer sessions (approximately 30-60 minutes) focused on Whole Health. All peer sessions at all levels will use a semi-structured interview tool to inquire about Veterans’ goals and goal progress and other mental health, physical health, and social needs. The peer will facilitate referrals and connections with community resources as appropriate for Veterans’ individual needs throughout Whole Health STEPS.

The proposed levels of support are all existing Whole Health services tailored for a peer scope of work. The innovative aspect of Whole Health STEPS is packaging these services together in a stepped care model. These are all variations of existing services and there are no known risks to peer services or Whole Health services.

Peer contact including sessions and other contacts (e.g., reminders, brief check-ins, contact attempts) will be documented in the medical record. Peer sessions will occur either in person and/or remotely over the phone or via VA Video Connect depending on current safety guidelines for in person appointments and Veteran preference. Peer sessions will be audio-recorded using VA approved audio-recording software to ensure the intervention is being delivered correctly and understand how Whole Health STEPS is being delivered. VA approved audio-recording software will also be used at a treatment feedback interview so that Veteran responses can be analyzed.

